28.0 Appendices261.0 Study Summary

Study Title	Behavior, Biology, and Well-Being (BeWell) Study
Brief Summary	This study is a randomized controlled trial to investigate the impact of a 4-week, mobile meditation training app on symptoms of depression and psychological distress. Adults who have elevated depressive symptoms between the ages of 18 and 65 will be enrolled in the study for about 4 months. We will also recruit a sample of healthy (non-depressed) controls who will only complete baseline measures.
Number of study sites	1
Study Design	Participants will be randomized into one of three groups: Healthy Minds Program intervention group, active control group, and usual care group. The intervention and active control groups will use different versions of the mobile health app for four weeks. All participants will complete pre-intervention, weekly, post-intervention, and 3-month follow-up surveys and computerized tasks. Healthy control participants will not be randomized.
Primary Objective	Assess acceptability and efficacy of a 4-week mHealth meditation training program on depression symptoms.
Secondary Objective(s)	Investigate effects of the meditation training program on neurocognitive and biological processes implicated in depression and psychological distress and through which meditation training is hypothesized to operate. Understand baseline differences between participants with and without depression.
Research Intervention(s)/Investigational Agent(s)	Healthy Minds Program (HMP) – a mobile health meditation training program
Drugs/devices used on study (including any IND/IDE #)	Healthy Minds Program (HMP) – a mobile health meditation training program
Study Population	18-65 year olds with no significant experience with meditation
Sample Size	1,765 participants
Study Duration for individual participants	4 months
Study Specific Abbreviations/Definitions	mHealth = mobile health HMP = Healthy Minds Program

2.0 Background

2.1 Depression is highly prevalent and associated with extreme personal and societal costs. Meditation training reduces depression symptoms and psychological distress, but access to in-person programs is limited due to associated cost and lack of available services. The primary aim of this project is to investigate the efficacy of a 4-week mobile health (mHealth) meditation training program for adults with a wide range of depressive symptoms in an entirely remote randomized controlled trial (RCT).

2.2 We have conducted similar mHealth studies with educators in Wisconsin (IRB Protocol: 2020-0533) and undergraduate students at UW-Madison (IRB Protocol: 2020-1454). Both studies provided evidence that a large number of participants are willing to download and regularly use the HMP app as well as stay engaged in a longitudinal study.

2.3 Research on neurocognitive and biological mechanisms of meditation training in alleviating depression is at a preliminary stage, and an obstacle limiting research progress is over-reliance on retrospective self-report measures, which are vulnerable to a host of biases. This project will use gold-standard behavioral measures and explore novel measures of relevant neurocognitive and behavioral processes, namely pattern separation, self-referential thought, and video-based assessment of emotional well-being. Furthermore, the project will investigate effects on the gut microbiome (with stool samples) and inflammation (with dried blood spots), which reflect biological systems hypothesized to be mechanistically related to benefits of meditation and well-being training.

3.0 Study Objectives and Endpoints

3.1 Specific Aims

- Assess acceptability and efficacy of a 4-week mHealth meditation training program on candidate behavioral mechanisms of depression and psychological distress.
- Investigate effects of the mHealth meditation training program on behavioral and neurocognitive processes implicated in depression and psychological distress and through which meditation training is hypothesized to operate and improve well-being.
- Investigate effects of the mHealth meditation training program on biological processes implicated in depression and psychological distress and through which meditation training is hypothesized to operate and improve well-being.
- Compare depressed and non-depressed participants on self-report, behavioral, and biological measures.

3.2 Hypotheses

- The intervention participants will show larger reductions in psychological distress relative to usual care and active control participants during the intervention period and at follow-up.

PROTOCOL TITLE: Behavior, Biology, and Well-Being (BeWell) Study

- The intervention participants will show improved pattern separation behavior relative to usual care and active control participants during the intervention period at post-intervention and at follow-up.
- The intervention participants will show reduced self-referential processing (e.g., first-person pronoun use) and greater video-based indicators of well-being relative to usual care and active control participants during the intervention period at post-intervention and at follow-up.
- Speech indicators (e.g., I-talk, negative self-focused statements, and inflexible overly general thinking) evident in natural language will predict depression and task performance.
- Machine learning models will modestly predict depression (Spearman's rho $\geq .30$).
- The intervention participants will show greater changes in biological processes relative to usual care and active control participants during the intervention period at post-intervention and at follow-up.
- Depressed participants will show differences on behavioral and biological markers of depression at baseline relative to non-depressed healthy controls.

3.3 Primary and Secondary Study Endpoints

Primary Endpoint

- Scores on the Physical Health Questionnaire depression scale (PHQ-8)

Secondary Endpoint

- Symptoms of psychological distress (GAD-7, PROMIS Sleep Disturbance and Flourishing Index)
- Performance on the behavioral pattern separation task
- Self-referential thought measured by the video recording task

3.4 Primary and Secondary Safety Endpoints

N/A

4.0 Number of Participants

4.1

This study will enroll 1,500 participants at UW-Madison. There will also be a pilot of up to 15 participants. We will recruit approximately 250 healthy control participants who will complete baseline measures only.

4.2

The expectation is that we will have 20-50% attrition resulting in roughly 750-1200 participants completing the study.

4.3

Participants will be considered enrolled after randomization. Participants who leave the study early will not be replaced. Healthy control participants will only complete baseline measures.

5.0 Inclusion and Exclusion Criteria

5.1 Screening

The screening survey will be accessed and completed in REDCap after potential participants learn more about the study and decide to continue with the screening process. Potential participants will be informed via a REDCap email of their eligibility up to 1 year after completing the screening surveys. This timeframe will be helpful to manage the unpredictability of participant recruitment and ensure that participants are enrolling in the study at a manageable rate for study activities that require staff time (e.g., clinical interview, sending and receiving biosample kits). If it has been 30 or more days since participants completed screening, they will be asked to complete the screening again before being invited to enroll. They will receive an email inviting them to do so. This email will be sent from the study email address (e.g., [contact]). Screening data will be retained for all potential participants regardless of whether or not they enroll in order to keep a record of reasons individuals are not eligible for the study for reporting purposes (e.g., consort diagram). Any identifiers will be removed from the screening data of individuals who are not eligible for the study. Contact information will only be retained from individuals who are eligible for the study.

5.2 Inclusion Criteria

Randomized participants:

- Age 18 to 65
- Proficient in English
- Able to provide informed consent
- Have access to a smartphone that can download apps from Google Play or the Apple App Store

Indicate interest in participation after being informed of restrictions to payment

- PHQ-8 or PHQ-9 ≥ 5

Healthy control participants:

- Age 18 to 65
- Proficient in English
- Able to provide informed consent
- Have access to a smartphone that can download apps from Google Play or the Apple App Store

Indicate interest in participation after being informed of restrictions to payment

- PHQ-8 or PHQ-9 < 5

5.3 Exclusion Criteria

Exclusion criteria apply to both randomized participants and healthy control participants.

- Regular daily meditation practice for past 6 months or regular weekly meditation practice for past 12 months
- Attended a meditation retreat or a yoga/body practice retreat with a significant meditation component
- Previous use of Healthy Minds Program app
- Current suicidal intent and/or high self-injury risk (determined from the interview)
- Self-reported history of psychosis
- Self-reported history of mania
- Current psychopathology that interferes with study participation as assessed by interview
- Living or traveling outside the US during the whole study participation period (trips outside US after the interview phase is not an exclusion)
- AUDIT score ≥ 13 for women and AUDIT score ≥ 15 for men
- DUDIT score ≥ 8 for women and men

5.4 Specific Population

We will recruit individuals with a wide range of depressive and psychological distress symptomatology. We expect the sample to be demographically representative of the overall population of the United States. The U.S. Census population estimates for July 2019 are 1.3% American Indian or Alaska Native, 5.9% Asian, 13.4% Black or African American, 18.5% Hispanic or Latino, 0.2% Native Hawaiian or Other Pacific Islander, 76.3% White, and 2.8% two or more races.

6.0 Special Populations

6.1

- Children/Minors
- Pregnant persons / fetuses (HRP-412 – CHECKLIST – Pregnant Women; HRP-413 – CHECKLIST – Non-Viable Neonates; HRP-414 – CHECKLIST – Neonates of Uncertain Viability)
- Prisoners
- Participants with impaired decision-making capacity

N/A

6.2

- Non-English speaking participants
- Illiterate or Low Literacy participants

PROTOCOL TITLE: Behavior, Biology, and Well-Being (BeWell) Study

- Participants with visual or hearing impairments
- Status Relationship: Individuals with a status relationship with the PI or other study team members (e.g., employees, students, family members)

N/A

6.3

- Individuals who are receiving inpatient or outpatient services for mental illness, developmental disability, or alcohol and other drug abuse (AODA)
- Individuals who are protectively placed by a court in a treatment facility
- Veterans/Military Personnel
- Emancipated minors
- Anyone especially vulnerable to manipulation or inducements for participation as a result of their illness or socioeconomic condition

N/A

7.0 Recruitment Methods

7.1 Sources of Participants

We will recruit from various sources. These sources may include the community, local and national mental health clinics, research recruitment services and from the Participant Registry at the Center for Healthy Minds (CHM; IRB Protocol: 2019-0330). We may also recruit using CHM social media and listservs.

7.2 Identifying Participants

Potential participants will self-identify in response to flyers, social media platforms, emails, web postings, research recruitment services (e.g., Prolific, Mturk, and/or ResearchMatch). We may send an email to individuals who have provided their contact information to CHM's Participant Registry; the email will include a link to the study page on REDCap. We may send messages to participants who have registered with recruitment services (e.g., ResearchMatch). Participants who are not eligible for the randomized portion of the study due to low depression symptoms (i.e., PHQ-8 or PHQ-9 < 5) may be invited to participate as a healthy control participant. We may write or have written articles about our study to be published in print or online media (e.g., Madison 365).

7.3 Recruitment Method

Recruitment materials may be shared with outside groups (e.g., universities), local and national mental health clinics and organizations (e.g., NAMI, Mental Health America), as well as posted at various local businesses (e.g., libraries, stores, and restaurants) up to several times throughout the year and shared by word of mouth. A web posting of the study may be included on CHM's website and social media ads may be placed on various social media platforms (e.g., Facebook, Twitter, Instagram) up to several times per year. We may also utilize email listservs at UW-Madison and other institutions, research recruitment services, as well as access CHM's Participant Registry to recruit participants via email up to several times per year. Our recruitment video may be posted on

PROTOCOL TITLE: Behavior, Biology, and Well-Being (BeWell) Study

third parties as well (e.g., WithPower.com). Past and/or currently enrolled participants may be invited to share recruitment materials with others. Participants will be informed that sharing recruitment materials is voluntary and unrelated to their study participation.

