7.4 Recruitment Materials

We may use flyers, web postings, social media ads, emails and a video posted on the REDCap study page to inform potential participants about the study. Materials will include a study email address for individuals to use if they have questions about the study. Recruitment will occur on a continuous basis throughout the 3-year study.

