11.0 Study Intervention

11.1

The study intervention will be the Healthy Minds Program (HMP), a 4-week mobile health meditation training augmented with depression-specific content. The HMP was developed by our affiliated non-profit organization, Healthy Minds Innovations, Inc (HMI). The HMP is designed to promote and protect psychological well-being through sustainable skills training, with instruction administered through a curriculum of high-quality guided practices. The HMP is based on research on eudaimonic well-being (e.g., environmental mastery, purpose) and brain-based skills that underlie these qualities (e.g., regulation of attention, mental flexibility). The HMP has >100 guided audio practices that address 4 constituents of well-being: awareness, connection, insight, and purpose. The intervention and active control groups will download and use a study specific version of the HMP immediately after randomization. The intervention group will have access to and instructed to listen to both the lessons and meditations (guided practices). The active control group

PROTOCOL TITLE: Behavior, Biology, and Well-Being (BeWell) Study

will have access to and instructed to listen to the lessons only (meditation practices are not included). The intervention and active control groups will use the HMP for four weeks. The active control group and the usual care group will be given the opportunity to download and use the full HMP after they finish their 3-month follow-up assessment.

The following usage data is recorded: date, time, duration, device type, lesson or practice, week, foundation (awareness, connection, insight, or purpose), and name of lesson or practice.

Participants listen to lessons and/or practices and occasionally answer pre and post questions using their smartphones.

This study requested a non-significant risk (NSR) determination for the use of the HMP. Use of the HMP may mitigate symptoms of depression, anxiety and/or stress but has not shown to pose a risk to health or safety. Below is a copy of the NSR letter.

Request for a Non-Significant Risk Determination from the IRB for an Investigational Device

UW-Madison Health Sciences IRB:

Please accept this letter as a request for non-significant risk (NSR) determination for the investigational device evaluation described in the IRB submission titled “BeWell Study”.

The FDA defines significant risk devices as follows (21 C.F.R. § 812.3(m)):

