13.0 Procedures Involved

13.1 Study Design

After potential participants are informed of their eligibility, they will be invited to complete the following steps:

1. Consent Process. Individuals will read a consent script in REDCap and are given the opportunity to reach out to study staff if they have any questions or concerns about study procedures before clicking on the box indicating interest in participating in the study.
2. Pre-Intervention Assessment (Timepoint 1). A REDCap link for these surveys and games (behavioral task and video task) will be sent after consent is completed. It will take approximately 60-90 minutes to complete these measures. Potential participants will be given two weeks to complete this assessment. In order to increase study retention, only those who complete this assessment will be invited to subsequent parts of the study. A microbiome and blood spot collection kit will be mailed to participants to be completed before randomization occurs. The kit needs to be returned within one month of completing the surveys and games to continue with the randomization step.
3. Interview. The participant will undergo an interview conducted by research staff who are trained in interviewing techniques and supervised by qualified study personnel with mental health expertise. The interview will consist of the depression and related modules of the Structured Clinical Interview for DSM-5 Research Version (SCID-5-RV). The interview will be done via phone or video and will take approximately 60 minutes to complete. Participants may be sent an email to confirm their current phone number, interview time, and/or other details to assist with interview scheduling.
4. Randomization. Participants will be assigned to one of three groups: approximately two-fifths to the HMP intervention group, approximately two-fifths to the active control group, and approximately one-fifth to the usual care group. Randomization will be done in REDCap (either immediately after the interview or within a few days if consultation with a study PI or Co-I is needed; the microbiome and blood spot kit need to be returned before randomization). A REDCap alert will inform participants of group status immediately after randomization along with instructions for downloading HMP for those in the intervention and active control groups.

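### Section 7.3 lets participants who know their arm be invited to recruit others while still in the trial, with no limit on timing or relationship and no stated record of who is linked to whom

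*Combined protocol and SAP*

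**What the plan says.** On recruitment, section 7.3 states that "Past and/or currently enrolled participants may be invited to share recruitment materials with others". The only condition it adds is "Participants will be informed that sharing recruitment materials is voluntary and unrelated to their study participation". It sets no limit by timing, arm or relationship. Section 7.4 adds "Recruitment will occur on a continuous basis throughout the 3-year study", and section 12.1 puts each person's participation at about four months, so a referrer and a recruit can overlap.

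On what a referrer knows and holds, section 4.3 counts a person as enrolled once randomized. Section 13.1 says "A REDCap alert will inform participants of group status immediately after randomization", and section 11.1 says "The intervention and active control groups will download and use a study specific version of the HMP immediately after randomization". The HMP version has lessons and meditations; the active-control version has lessons only. App users may carry on with their version after week 4 (section 13.1, item 6).

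On keeping the arms apart, section 11.1 says "The active control group and the usual care group will be given the opportunity to download and use the full HMP after they finish" the 3-month follow-up. Previous HMP use is an exclusion (section 5.3). A Meditation and App Usage Questionnaire is marked at pre- and post-intervention, but not at 3-month follow-up (section 13.3, measures table).

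On analysis, section 20.4 plans linear mixed models to handle non-independence without naming a grouping level. No section describes recording referral source or household, or using the app-usage answers in an analysis.

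**The concern.** The plan holds the meditations back from both control arms until follow-up is over, and that separation is the whole contrast between HMP and active control. Recruiting through people who are still in the trial works against it. A control participant who knows an HMP participant may hear or borrow the meditations. A lessons-only participant who compares notes learns what their version leaves out. Either could move answers on a self-reported depression scale, and could affect retention.

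The existing safeguards do not cover this route. The prior-use exclusion catches exposure before enrollment, not sharing after it. The usage questionnaire could reveal exposure during the four weeks, but the hypotheses in section 3.2 run to follow-up, where it is not given. If links between participants are not stored, their effect cannot be examined once the data are in.

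**Working it through.** **The plan's own figure first.** Section 20.2 gives 1,500 randomized at 2:2:1 (600, 600, 300), 20% dropout (480, 480, 240 left), and 80% power for d = 0.20 against active control and d = 0.28 against usual care. Alpha is not stated. With SD 1, power = Φ(d / √(1/n₁ + 1/n₂) − z).

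- Active control, two-sided 5%: √(2/480) = 0.0645; 0.20/0.0645 = 3.098; Φ(3.098 − 1.960) = 87.3%.
- Usual care, two-sided 5%: √(1/480 + 1/240) = 0.0791; 0.28/0.0791 = 3.542; Φ(3.542 − 1.960) = 94.3%.

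So the stated 80% is not reproduced at two-sided 5%. At two-sided 2.5% the first is 80.4%, but the second is 90.3%. That mismatch is a separate matter; two-sided 5% is used below unless stated.

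**Which linked pairs matter.** Section 13.1 allocates "approximately two-fifths to the HMP intervention group, approximately two-fifths to the active control group, and approximately one-fifth to the usual care group". For two people randomized independently:

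| Pair | Probability |
|---|---|
| HMP and active control | 2 × 0.4 × 0.4 = 0.32 |
| HMP and usual care | 2 × 0.4 × 0.2 = 0.16 |
| Active control and usual care | 2 × 0.4 × 0.2 = 0.16 |
| Same arm | 0.16 + 0.16 + 0.04 = 0.36 |

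The pairs that put the meditations next to a control participant are the first two: 0.32 + 0.16 = 48%.

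**Illustrative dilution.** The documents give no referral or sharing rates, so these are assumptions: 10–20% of participants referred by an enrolled person, 40% of those referrers in HMP, and 25–100% of the linked controls gaining the full HMP effect.

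- Low end: c = 0.10 × 0.40 × 0.25 = 1%.
- High end: c = 0.20 × 0.40 × 1.00 = 8%.

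The observed difference becomes d(1 − c). For HMP against active control at c = 8%, d = 0.20 × 0.92 = 0.184; 0.184/0.0645 = 2.851; Φ(2.851 − 1.960) = 81.3%.

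| c | HMP vs active control | HMP vs usual care |
|---|---|---|
| 0 | 87.3% | 94.3% |
| 5% | 83.7% | 92.0% |
| 8% | 81.3% | 90.3% |
| 10% | 79.6% | 89.0% |
| 20% | 69.8% | 80.9% |

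Power crosses 80% at c of about 9.6% (active control) and 20.9% (usual care). There is less room under harsher settings. With the 50% attrition that section 4.2 also allows (300, 300, 150 left), power is 68.8% and 80.0% before any dilution, and 59.7% and 71.2% at c = 10%. At two-sided 2.5% with 20% dropout, the active-control comparison goes from 80.4% to Φ(2.851 − 2.241) = 72.9% at c = 8%.

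This formula counts only controls recruited by an HMP referrer. A control referrer whose recruit lands in HMP is not counted.

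**Correlated outcomes.** Type I error for HMP against active control was simulated with individually randomized referral clusters (1,200 people, 4,000 runs per setting; 20–100% of the sample in clusters of 2–5, intraclass correlation 0.1–0.3). It was 4.7–5.3%, against 5.6% with no clustering. With a Monte Carlo standard error of √(0.05 × 0.95/4000) = 0.34 percentage points, this shows no inflation.

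**The case against.** The strongest case on the other side is that one permissive sentence, among many recruitment channels, has been given more weight than it can bear. Several stronger readings are tempting, and the documents do not support them.

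- *Correlated outcomes invalidate the test.* Links formed by referral are not aligned with arm when individuals are randomized, and the simulation found no inflation. A cluster-trial design effect would be wrong here.
- *64% of pairs are a problem because they fall in different arms.* That total includes the 16% that join active control with usual care, where neither person has the meditations through the study. Likewise, four-fifths of participants hold an app, but only two-fifths hold the meditations during the study.
- *Recruits will be friends or household members.* Section 7.3 says only that materials may be shared with others. Some recruits would score below 5 on the PHQ and could join only as non-randomized healthy controls.
- *The plan has no safeguard at all.* It excludes prior users and asks about app use before and after the intervention. Consent pages are not in the material reviewed, and the screening questions are listed only by example. A referral question or a request not to share could exist there.

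It is also fair to say that the app is free, and that withdrawing participants are told so (section 15.3), so referral is not the only route to contamination.

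A further objection concerns the remedy. Limiting invitations to people who have finished does not protect the recruit, because completers of all three arms can hold the full HMP. Under the same assumptions, the 40% factor could rise to 100%, giving c up to 0.20 × 1.00 × 1.00 = 20% and power of 69.8%. Past participants may already be invited under the present text, so the limit adds no new route, but a screening question about current participants alone would miss these links.

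All of this stands, and it lowers the priority. What remains is that referral by participants still in the trial is allowed without limits, and the plan describes no way to identify or examine the resulting links.

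**Conclusion.** The concern holds as a minor point, with moderate confidence. The text is clear that randomized participants who know their arm may be invited to recruit while still in the study, and it describes no limit on timing or relationship and no recording of links. The harm to expect is interference between linked participants, mainly diluting the HMP contrast towards no difference.

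Its size cannot be estimated from the documents. The 48% follows from the allocation ratio and independent randomization. The fall from 87% to 81% rests on an assumed 8% of controls gaining the entire HMP effect, 480 per arm and two-sided 5%; at the 1% end, power is almost unchanged. A reader might infer that power is lost below the plan's stated 80%, or that false positives rise. The first happens only with heavier contamination, higher attrition or a stricter alpha than that illustration uses, and the second is not supported.

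**What to change.** 1. In section 7.3, do not invite participants who are still in their own study period to share recruitment materials. This protects the referrer's data.
2. Add one web-screen item asking whether the person lives with, or was referred by, any current or past participant. Past participants must be included, because the first step does not protect the recruit from a completer who holds the full HMP.
3. Do not randomize a second member of a household while the first is in follow-up.
4. Store the link with the study data, and pre-specify in section 20 a sensitivity analysis of the PHQ-8 comparisons that excludes linked participants.

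The cost is one changed sentence, one screening item, a household check before randomization and one extra analysis. Word-of-mouth recruitment may be slightly slower. No change to the sample size or to the main model is needed on this account.
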